1. BACKGROUND AND DESIGN

Atropine 1% is very effective in slowing myopia progression, but it is not popular because of its unwanted side effects of pupillary dilation and cycloplegia and possible rebound effect. Atropine eye drops at a concentration of 0.01% are expected to be safe and well tolerated. This is supported by evidence from other trials that have employed the same and other more potent anti-muscarinic agents (e.g. 1% atropine; pirenzepine), and the well-established safety profile of atropine use in ophthalmology.

This is a multicentre, randomised, double-masked, placebo-controlled, superiority trial, with 2:1 allocation of intervention and control (atropine: placebo).

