1.3 Study Objectives

The primary objective is:

 To evaluate the efficacy of 0.01% atropine eye drops to reduce the progression of myopia in children after 24 months of treatment.

The secondary objectives are:

- To evaluate the safety and tolerability of low dose atropine eye drops in terms of difficulties with near vision and reading, local discomfort and stinging of eye drops, photophobia, and occurrence of allergic reactions.
- To determine the mechanism of action of atropine eye drops. Specifically, we will evaluate if atropine has an effect on central axial length of the eye, position of the lens, peripheral retinal defocus and use of spectacle correction.

The exploratory objectives are:

• To explore the influence of other factors in the progression of myopia, including accommodation, chorio-retinal thickness at the macula, peripheral axial length, hours of outdoor activity, iris colour, ethnicity, and family history.

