1.4 Inclusion and Exclusion Criteria

Patients will be eligible to participate in the study if they fulfil the following criteria below. Eligibility will be confirmed by a medically qualified doctor and documented on the eligibility checklist form.

Inclusion Criteria

- 1. Age 6-12 years (at the time of consenting)
- 2. Myopia of -0.5D or greater (spherical equivalent refractive error) in both eyes
- 3. Best-corrected distance visual acuity (BCDVA) 0.20 logMAR or better in both eyes

Exclusion Criteria

- 1. Children with other ocular morbidities
- 2. Myopia of -10D or greater in either eye
- 3. Astigmatism of 2D or higher in either eye
- 4. Amblyopia
- Significant health problems that can compromise the ability to attend research visits or complete the trial
- 6. Other factors that may compromise the ability to attend the research appointments
- 7. Parents or children with poor understanding of the English language
- 8. Children enrolled in other interventional trials*
- 9. Allergy or hypersensitivity to atropine or excipients
- 10. Previous use of atropine eye-drops, prior or current use of Ortho-K contact lenses or contact lenses with dual focus, multifocal or extended depth of focus lens design
- 11. Children or Parents / Guardians with latex allergy as the dropper used to administer the eye-drop contains latex

*Children enrolled in observational studies are potential candidates for CHAMP UK. Whether or not children enrolled in CHAMP UK are also involved in other observational studies is at the discretion of the CHAMP UK local Principal Investigator (PI) and should be considered when the burden on participants is not expected to be onerous. Coenrolment with other studies should be documented in the Case Report Form (CRF).

Full details of the background to the trial and its design are presented in the protocol.

Doc No: ST06-RD01 Page **6** of **47**

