Reaction (SUSAR) product in question set out: - in the case of a product with a marketing authorisation, in the SPC for that product - in the case of any other investigational medicinal product, in the IB relating to the trial in question. Per protocol Population The per protocol population is defined as participants with overall study drug adherence of at least 80% using MEMs data. Intention to treat The intention to treat population is defined as all participants who are		
- in the case of a product with a marketing authorisation, in the SPC for that product - in the case of any other investigational medicinal product, in the IB relating to the trial in question. Per protocol Population The per protocol population is defined as participants with overall study drug adherence of at least 80% using MEMs data. Intention to treat The intention to treat population is defined as all participants who are		
product - in the case of any other investigational medicinal product, in the IB relating to the trial in question. Per protocol Population The per protocol population is defined as participants with overall study drug adherence of at least 80% using MEMs data. Intention to treat The intention to treat population is defined as all participants who are	Reaction (SOSAR)	
- in the case of any other investigational medicinal product, in the IB relating to the trial in question. Per protocol Population The per protocol population is defined as participants with overall study drug adherence of at least 80% using MEMs data. Intention to treat The intention to treat population is defined as all participants who are		
the trial in question. Per protocol Population The per protocol population is defined as participants with overall study drug adherence of at least 80% using MEMs data. Intention to treat The intention to treat population is defined as all participants who are		
Per protocol Population The per protocol population is defined as participants with overall study drug adherence of at least 80% using MEMs data. Intention to treat The intention to treat population is defined as all participants who are		
adherence of at least 80% using MEMs data. Intention to treat The intention to treat population is defined as all participants who are	Per protocol Population	
Intention to treat The intention to treat population is defined as all participants who are	1	
	Intention to treat	

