Doc No: ST06-RD01 Page **13** of **47**

7. **ANALYSIS PRINCIPLES**

Baseline characteristics and follow up measurements will be summarised as mean and standard deviation (SD), median and inter-quartile range (IQR) or numbers and frequencies (%) as appropriate, depending on the scale of measurement and distribution. Analysis will be based on both the intention to treat (ITT) principle and per protocol (PP) analysis. PP analysis will explore results in those who had at least 80% adherence to the study drug. A p-value <0.05 will be considered as statistically significant.

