8.4 Trial treatment

- · Time from randomisation to start of study drug, mean (sd) by treatment arm
- Medical Events Monitoring System (MEMS): Average adherence (%), average drug holidays and average overdosing over total study time period, mean (sd) by treatment arm
- Reasons for termination of study drug: number (%) by treatment arm for study drug related AE, study drug related SAE, study drug expiry date, patient request, clinicians request and other
- Protocol deviations/violations: number (%) by treatment arm for eligibility, study drug administration (participant reported), study drug administration (MEMS data), safety reporting (AE/SAE), visit outside schedule OR missed visit, assessment not done and other
- Premature withdrawals: number (%) by treatment arm for adverse event, serious adverse event, protocol deviation, lost to follow up, withdrawal of patient consent, death, withdrawal at clinician's request and other
- Did not receive allocated treatment (which includes those who received no treatment), number
 (%) by treatment arm
- Received treatment of other group, number (%) by treatment arm

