Pupil diameter ^a	$xx.x \pm xx.x n =$	$xx.x \pm xx.x n=$	$xx.x \pm xx.x n =$			
Left eye	$xx.x \pm xx.x n=$	$xx.x \pm xx.x n=$	$xx.x \pm xx.x n=$			
Right eye	$xx.x \pm xx.x n=$	$xx.x \pm xx.x n=$	$xx.x \pm xx.x n=$			
Spectacle correction						
Yes	n(%)	n(%)	n(%)			
No	n(%)	n(%)	n(%)			
Frequency of spectacle correction						
All day	n(%)	n(%)	n(%)			
Sometimes	n(%)	n(%)	n(%)			
Contact lens use						
Yes	n(%)	n(%)	n(%)			
No	n(%)	n(\)	n(%)			
Frequency of contact lens use						
All day	n(%)	n(%)	n(%)			
Sometimes	n(%)	n(%)	n(%)			

Reported as frequency (percentage), mean \pm SD, or median (p25 to p75) based on the distribution of the data. ^aMean of two eyes, ^bnot weighted.

Doc No: ST06-RD01 Page **26** of **47**

Table XXX: Treatment after trial entry

	Atropine sulfate N=	Placebo N=
Time from randomisation to start of study drug	xx.x (xx.x)	xx.x (xx.x)
MEMS data ^a		
Adherence	xx.x (xx.x)	xx.x (xx.x)
Drug holidays	xx.x (xx.x)	xx.x (xx.x)
Over dosing	xx.x (xx.x)	xx.x (xx.x)
Reasons for termination of study drug		
Study Drug related AE	n (xx.x%)	n (xx.x%)
Study Drug related SAE	n (xx.x%)	n (xx.x%)
Study Drug Expiry Date	n (xx.x%)	n (xx.x%)
Patient Request	n (xx.x%)	n (xx.x%)
Clinician's Request	n (xx.x%)	n (xx.x%)
Other	n (xx.x%)	n (xx.x%)
Protocol deviations/ violations		
Eligibility	n (xx.x%)	n (xx.x%)
Study Drug Administration (Participant reported) ^b	n (xx.x%)	n (xx.x%)
Study Drug Adminstration (MEMS data) ^b	n (xx.x%)	n (xx.x%)
Safety reporting (AE/SAE)	n (xx.x%)	n (xx.x%)
Visit outside schedule OR missed visit	n (xx.x%)	n (xx.x%)
Assessment not done	n (xx.x%)	n (xx.x%)
Other	n (xx.x%)	n (xx.x%)
Premature Withdrawals		
Adverse Event	n (xx.x%)	n (xx.x%)
Serious Adverse Event	n (xx.x%)	n (xx.x%)
Protocol deviation	n (xx.x%)	n (xx.x%)
Lost to Follow Up	n (xx.x%)	n (xx.x%)
Withdrawal of patient consent	n (xx.x%)	n (xx.x%)
Death	n (xx.x%)	n (xx.x%)
Other	n (xx.x%)	n (xx.x%)
Did not receive allocated treatment (which includes	, -7	, -7
those who received no treatment)	n (xx.x%)	n (xx.x%)
Received treatment of other group	n (xx.x%)	n (xx.x%)

^a MEMs data averaged over the total study time period. ^bIf the drops are missed 20% or more.

Doc No: ST06-RD01 Page **27** of **47**

Table XXX: Main Clinical Outcomes

	Similear Ot		ent Group	Unadjust	ed	Adjuste	d ^a	Adjusted	b
Variables		Atropine sulfate N=	Placebo N=	Mean difference (95% CI)	P value	Mean difference (95% CI)	P value	Mean difference (95% CI)	P value

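### The per-protocol set is defined by MEMS adherence alone, so it keeps children who received the other arm's drug or were ineligible at entry

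*Supplement*

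**What the plan says.** SAP section 4 (Definition of terms) states: "The per protocol population is defined as participants with overall study drug adherence of at least 80% using MEMs data". Section 7 (Analysis Principles) gives the same single condition with its purpose: "PP analysis will explore results in those who had at least 80% adherence to the study drug". No other section adds an exclusion or refers to the protocol for one.

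Section 8.4 and the appendix table on treatment after trial entry count, by arm, eligibility violations and children in the row "Received treatment of other group, number (%) by treatment arm". Nothing removes these children from the PP set. For the averaging window, section 8.4 reports adherence together with "average drug holidays and average overdosing over total study time period", and the table footnote says "MEMs data averaged over the total study time period".

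PP results stand beside ITT for the primary outcome and the other 24-month outcomes (8.5), the sensitivity analyses (8.6), the subgroups (8.7), the earlier visits (8.8) and the exploratory outcomes (appendix). The primary objective in section 1.3 is: "To evaluate the efficacy of 0.01% atropine eye drops to reduce the progression of myopia in children after 24 months of treatment".

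**The concern.** A PP result printed next to ITT will be read as the effect in eligible children who took their allocated drops. The definition does not secure that. Adherence measures use of a bottle. A placebo child who was dispensed atropine and used it faithfully passes the 80% test as easily as a child on the right drug, and so does a child who failed an entry criterion.

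The SAP does not say in which arm a wrong-drug child is analysed within PP. The natural reading is the randomised arm, and then that child pulls the two means together in the analysis meant to show the effect under good use. The trial team already holds both lists, so the set could be cleaned at almost no cost. If the rule is left open, the temptation is to decide on these children after the allocation is known.

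**Working it through.** **Inputs.** Section 5: control progression 0.8 D over 24 months, 40% reduction, planned arms of 193 and 96. Section 4: 80% threshold. Section 3.3, Table 1: study drug dispensed at baseline, 6, 12 and 18 months. Adherence window: total study period (8.4 and table footnote).

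**Planned contrast.** 0.40 × 0.8 D = 0.32 D, as the SAP states. Over two years this is 0.40 D/year in control and 0.60 × 0.40 = 0.24 D/year on atropine.

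**Wrong-arm children in PP.** Let a fraction c of one arm's PP children take the other drug for the whole period and be analysed as randomised. The PP difference is 0.32 × (1 − c). With the same fraction in both arms it is 0.32 × (1 − 2c). The values of c are assumptions, because the documents give none.

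| c | one arm | both arms |
|---|---|---|
| 1% | 0.317 D | 0.314 D |
| 2% | 0.314 D | 0.307 D |
| 5% | 0.304 D | 0.288 D |

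If all randomised children were in PP, one wrong-arm child would be 1/96 = 1.04% of the placebo arm (0.32/96 = 0.0033 D) or 1/193 = 0.52% of the atropine arm (0.32/193 = 0.0017 D). A smaller PP set raises each share a little. These figures assume the wrong drug throughout. If only one of the four dispensings was wrong and the effect accrues evenly, that child loses about a quarter of the contrast.

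**Ineligible children.** No arithmetic applies. The direction depends on which criterion was breached.

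**Final gap off drops.** With a 24-month denominator and prior adherence a, the longest final gap is 24 − 24 × 0.80 / a months:

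- a = 100%: 4.8 months
- a = 95%: 3.8 months
- a = 90%: 2.7 months
- a = 85%: 1.4 months
- a = 80%: 0 months

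A child who stops at month 18 has at most 18/24 = 75% and is already excluded. With full use to month 19.2 and even accrual, the loss for an atropine child is (0.40 − 0.24) × 0.4 year = 0.064 D, or 20% of 0.32 D for that child. If 5% to 20% of PP atropine children were that extreme (an assumption), the group difference would fall by 0.05 × 0.064 = 0.003 D to 0.20 × 0.064 = 0.013 D, which is 1% to 4%.

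**Does a late-adherence rule remove this?** Requiring 80% overall and also 80% in months 18–24 would still allow 1.2 months off late plus 3.6 months off earlier, again 4.8 months. With even accrual the loss is the same 0.064 D.

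**Denominator.** If adherence were taken over time on drug instead, a child who stopped at month 12 could score 100%. Section 4 says only that adherence is overall, so the window should be stated there.

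**The case against.** The best defence is that section 7 promises only a look at children with good adherence, and the definition delivers that. A set that also excludes other deviations is a common alternative, not the only valid one. Wrong-arm supply needs an error despite numbered, identical bottles and a randomisation email copied to pharmacy as a check before dispensing (6.2). Both counts are tabulated, ITT is unaffected, and the protocol, which might say more, is not among the documents.

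Much of this stands: it keeps the likely effect small and the point modest. It does not rescue the definition. One might read adherence to study drug as adherence to the allocated drug, but it is measured by MEMS data, which cannot tell one masked kit from another. The SAP gives its own definition and does not defer to the protocol.

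Two stronger readings are tempting and are not supported:

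- *That allowing 4.8 months off drops before the month-24 measurement is an error.* That gap is a ceiling requiring perfect prior use. Under even accrual the timing of missed drops does not matter. A special penalty for late stopping would need rebound or a similar timing effect. Section 1 does mention "unwanted side effects of pupillary dilation and cycloplegia and possible rebound effect", but of atropine 1%, not the 0.01% under trial.
- *That PP should also exclude children who start optical myopia control during the trial.* Section 1.4 bars "prior or current use of Ortho-K contact lenses or contact lenses with dual focus, multifocal or extended depth of focus lens design", but as an entry rule. The SAP lists contact-lens use only among baseline characteristics and does not show that lens design is recorded at follow-up; rules for the treatment period may sit in the protocol.

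Both exclusions would also select on events after randomisation that may depend on how fast a child progresses. Eligibility at entry precedes randomisation, and a dispensing error under masking is much less likely to be related to outcome.

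**Conclusion.** The point holds in a limited form. Adherence is the only PP criterion, so wrong-arm and ineligible children whom the SAP itself counts remain in a set reported beside ITT for the primary outcome. The PP difference shrinks by about 1% for each 1% of full-period crossover in one arm, assuming analysis as randomised and equal adherence otherwise. The documents give no crossover rate, and it is probably small. They also do not show that any such child exists; the claim is about what the definition admits.

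The permitted final gap off drops, 4.8 months at most and 2.7 months at 90% prior adherence, follows from averaging and is not a fault. It assumes a 24-month denominator and no credit for overdosing; the SAP does not say whether extra doses are capped. The primary ITT conclusion is untouched.

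**What to change.** In sections 4 and 7, define the PP population as participants who meet all of the following:

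1. eligible at entry;
2. received only the allocated treatment;
3. overall MEMS adherence of at least 80%, with the 24-month period as denominator.

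Set the flag before the allocation is revealed to those judging eligibility deviations, and report the number removed under each criterion by arm. In the same edit, reconcile a boundary: the footnote to the treatment table treats missing exactly 20% of drops as a deviation, while section 4 admits exactly 80% adherence to PP.

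A PP analysis that also requires adherence late in follow-up may be added as supplementary, labelled exploratory because it selects on events after randomisation.

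Cost: a few lines of SAP text and a revised flag from records already kept (MEMS logs, eligibility deviations, treatment received). The PP set becomes slightly smaller and its confidence interval slightly wider. ITT does not change.

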5. SAMPLE SIZE CALCULATIONS

We anticipate that the effect of atropine eye drops in a UK population will be smaller than the reported effect in Chinese populations, but assuming that atropine reduces the progression of myopia by at least 40% in 24 months from a control mean of -0.8D7 (40% of 0.8 is equivalent to a mean difference of -0.32D between intervention and control group at 24 months), using SD=0.7D, a correlation (interclass correlation coefficient) between eyes of 0.9 and a variation inflation factor of 1.9, we will need 97 participants in each group. Considering a dropout rate of 15% and that 10% of the recruited children will be Chinese, we will need a total of 289 participants: 193 atropine, 96 placebo (152 atropine, 76 placebo inflated by a variance inflation factor of 1.9) to detect this difference in the non-Chinese population with 90% power.

Justification: In a study of 400 Chinese children evaluating the effect of 24 months of 1% atropine eye drops, myopia progression was -1.20 +/- 0.69 D in the placebo control group, and -0.28 +/- 0.92 D in the atropine group. We have assumed that progression of myopia and efficacy of atropine will be less in UK children than in Chinese children2.

Progression of myopia of untreated children was estimated from the control groups of randomized controlled trials for myopia. The following progression data have been reported:

- Katz 2003⁴ (Chinese race): progression of -1.28D (SD 0.78) D after 2 years (control was spectacles)
- Edwards 2002⁵ (Chinese race): progression of -1.26D (SD 0.74) D after 2 years (control was single vision lenses)
- Chua 2006³, ATOM study (Chinese race): progression of -1.20D (SD 0.69) after 2 years (control was placebo drops)
- Hyman 2005⁶, COMET trial (children of mixed races, with whites being the most common ethnicity): progression of 1.32D after 3 years (standard error 0.04) (control was single vision lenses)
- Breslin 2013⁷, In an observational study from the UK, myopia progression was 1.14D after 3 years.

Doc No: ST06-RD01 Page **12** of **47**

6. RANDOMISATION AND BLINDING

6.1 Randomisation

All participants who agree to join the study will be assigned a unique Participant Identification Number. Eligible participants will be randomised using a 2:1 allocation ration into the two groups (193 atropine: 96 placebo). Randomisation will use the remote automated computer randomisation application, Sealed Envelope, ensuring allocation concealment. Randomisation will be computer-allocated using a minimisation algorithm to ensure balanced allocation of participants across the two treatment groups. Minimisation will be by centre, ethnic background (white/non-white), and severity of myopia (less than - 3D in either eye / -3D or greater in the eye with more severe myopia). The unit of randomisation will be the participant (not the eye).

6.2 Blinding and Allocation Concealment

The study will be conducted in a double-masked fashion. Study treatment assignment will be masked for both the investigators and the participant. The atropine and placebo eye drops will be packaged in identical bottles and labelled with a unique identification number so that the investigator and participants are unable to identify the contents.

To maintain the overall quality of the trial, unmasking (i.e. unblinding) should only occur in exceptional circumstances when knowledge of the group allocation is absolutely essential in a medical emergency for further management of the participant or where information is required for expedited reporting of a SUSAR. If time permits, the local PI should attempt to contact the Chief Investigator prior to unmasking. On the occurrence of any such event, the local Principal Investigator (PI) will request for the participant to be unmasked through the Sealed Envelope system. If they experience any difficulties the PI should contact the Northern Ireland Clinical Trials Unit (NICTU) to request emergency unmasking of the participant via the randomisation system (Sealed Envelope) during usual office hours. Where emergency unmasking is required out of hours, the local PI should contact the Chief Investigator and if they are unavailable, the BHSCT Pharmacy Oncall Service as detailed in the study unmasking guideline. In the event that unmasking occurs, the participant may discontinue the study drug but will remain on the trial unless they decide to withdraw or the local PI feels that this is necessary. Where unmasking has occurred, this should be fully documented by the site and the NICTU informed.

The randomisation list will be generated by Sealed Envelope and group allocation will only be visible to those with Administrator access in the Trial Management team in NICTU. The randomisation email generated by Sealed Envelope which is sent to the local researcher will provide the study drug kit number to be prescribed but will not reveal the group to which the participant has been assigned. The local researcher will access the automated randomisation system to obtain the kit number for each participant. Upon receipt of the randomisation email from Sealed Envelope, a prescription will be completed detailing the study drug kit number to be dispensed. A copy of the randomisation email will also be sent to the site pharmacist as a quality control check prior to dispensing.

Doc No: ST06-RD01 Page **13** of **47**

7. **ANALYSIS PRINCIPLES**

Baseline characteristics and follow up measurements will be summarised as mean and standard deviation (SD), median and inter-quartile range (IQR) or numbers and frequencies (%) as appropriate, depending on the scale of measurement and distribution. Analysis will be based on both the intention to treat (ITT) principle and per protocol (PP) analysis. PP analysis will explore results in those who had at least 80% adherence to the study drug. A p-value <0.05 will be considered as statistically significant.

